## Medical History

7. Current evidence of Common Terminology Criteria for Adverse Events (CTCAE) Grade > 1 toxicity (due to prior anticancer therapy) before the start of treatment, except for hair loss and those Grade 2 toxicities listed as permitted in other eligibility criteria.
8. Current evidence of significant (CTCAE Grade  $\geq 2$ ) infection or wound within 4 weeks before the start of treatment.
  - a. Subjects with Grade 2 infection that has stabilized or improved with oral anti-infectives before the start of treatment may be eligible at the sponsor's discretion.
9. Known or suspected hypersensitivity to the study drug or excipients contained in the study drug formulation.
10. Current evidence of hypersensitivity or other underlying illness requiring systemic corticosteroids at doses > 20 mg/day prednisone equivalent
11. Current evidence of uncontrolled human immunodeficiency syndrome (HIV), HBV or HCV at screening. Serology testing is not required if seronegativity is documented in the medical history, and if there are no clinical signs suggestive of HIV or hepatitis infections, or suspected exposure. The following exceptions apply for subjects with positive viral serology:
  - a. Subjects with HIV and an undetectable viral load and CD4+ T-cell (CD4+) counts  $\geq 350$  cells/mL may be enrolled, but must be taking appropriate opportunistic infection prophylaxis, if clinically relevant.

- b. Subjects with positive HBV serology are eligible if they have an undetectable viral load and the subject will receive antiviral prophylaxis for potential HBV reactivation per institutional guidelines.
- c. Subjects with positive HCV serology are eligible if quantitative PCR for plasma HCV RNA is below the lower limit of detection. Concurrent antiviral HCV treatment per institutional guidelines is allowed.

12. Current evidence of incomplete recovery from surgery or radiotherapy before start of treatment, or planned surgery or radiotherapy from the start of treatment until the EoT visit, except minor elective surgery deemed acceptable by the investigator or palliative radiation therapy to non-target lesions, as described in [Section 6.5](#).

13. History of cardiovascular, renal, hepatic or any other disease within 3 months before the start of treatment that in the investigator's opinion, may increase the risks associated with study participation or require treatments that may interfere with the conduct of the study or the interpretation of study results.

14. History or current evidence of neoplastic disease that is histologically distinct from NHL, except cervical carcinoma in situ, superficial noninvasive bladder tumors, curatively treated Stage I-II non-melanoma skin cancer. Subjects with prior, curatively treated cancer > 2 years ago before the start of treatment can be enrolled.

15. Current evidence of new or growing brain or spinal metastases during screening. Subjects with known brain or spinal metastases may be eligible if they:

- a. Had radiotherapy or another appropriate therapy for the brain or spinal metastases; concurrent prophylactic treatment is allowed
- b. Neurologic symptoms must be stable and no worse than Grade 2
- c. Have evidence of stable brain or spinal disease on CT or MRI scan obtained within 4 weeks before signing the informed consent and compared with prior imaging results
- d. Do not require steroid therapy (or, if applicable, have been stable on dose of no more than prednisone 20 mg/day or equivalent by C1D1)

16. Women who are pregnant or breastfeeding.

17. History of non-adherence to the schedule of procedures or medication use.

18. Current evidence of Graft vs Host Disease

19. History or current evidence of significant cardiovascular disease including, but not limited to, the following conditions:

- a. Unstable angina (symptoms of angina at rest) or new-onset angina within 3 months before the start of treatment.
- b. Arterial thrombosis or pulmonary embolism within 3 months before the start of treatment.
- c. Myocardial infarction or stroke within 3 months before the start of treatment.
- d. Pericarditis (any CTCAE grade), pericardial effusion (CTCAE Grade  $\geq 2$ ), non-malignant pleural effusion (CTCAE Grade  $\geq 2$ ) or malignant pleural effusion (CTCAE Grade  $\geq 3$ ) within 3 months before the start of treatment with MT-3724.

- e. Congestive heart failure (New York Heart Association [NYHA] Class III or IV) at screening or left ventricular ejection fraction (LVEF)  $\leq 45\%$ , assessed by echocardiogram (ECHO) or multigated acquisition (MUGA) scan within 1 month before starting study treatment (inclusion of subjects with LVEF between 40% to 45% should be discussed with the medical monitor and approved by the sponsor). (ECHO or MUGA performed within 6 months before screening and at least 28 days after the last cancer therapy is acceptable provided the subject has not received any potentially cardiotoxic agents since then).
- f. Cardiac arrhythmia requiring anti-arrhythmic therapy at screening. Subjects receiving digoxin, calcium channel blockers, or beta-adrenergic blockers are eligible at the investigator's discretion after consultation with medical monitor and sponsor if the dose has been stable for  $\geq 2$  weeks before the start of treatment with MT-3724. Subjects with sinus arrhythmia and infrequent premature ventricular contractions are eligible at the investigator's discretion.

### 5.3 Screen Failures

Screen failures are defined as subjects who consent to participate in the clinical study but are not subsequently entered in the study. A minimal set of screen failure information is required to ensure transparent reporting of screen failure subjects to meet the Consolidated Standards of Reporting Trials publishing requirements and to respond to queries from regulatory authorities. Minimal information includes demography, screen failure details, eligibility criteria, and any serious adverse event (SAE) deemed related to a protocol screening procedure.

Individuals who do not meet the criteria for participation in this study (screen failure) may be rescreened. Informed consent is required before subjects can be rescreened if outside the original 35-day screening window. See [Section 10.1.4](#) for Informed Consent Process details.

## 6 STUDY TREATMENT

### 6.1 Study Treatment(s) Administered

As a standard precaution for all study drugs, subjects must be treated and observed in an area with equipment for resuscitation including assisted ventilation and emergency treatments or have access to emergency facilities through an emergency call. Adequate management and treatment of infusion-related reaction (IRR), anaphylactic reaction or other hypersensitivity events according to institutional guidelines must always be assured during the treatment period.

#### 6.1.1 Investigational Product: MT-3724

MT-3724 is the only investigational medicinal product in this study.

MT-3724 will be supplied as a sterile aqueous solution (pH █) in a 2 ml vial containing 2.0 mL of MT-3724 (0.5 mg/ml) in a formulation buffer comprised of sorbitol █ mM), sodium citrate █ mM) and polysorbate-20 █ (%). Vials are shipped frozen. Each vial will be labeled with the

drug name, lot number, storage conditions, and US Food and Drug Administration (FDA)-required Investigational Product statement.

MT-3724 vials must be stored in a secure facility at [REDACTED] until thawed for use. It is recommended to use the thawed drug to prepare the final solution for infusion within 3 hours, although MT-3724 is stable at room temperature for up to 24 hours.

During preparation of the final solution for infusion, MT-3724 is diluted in [REDACTED] dextrose in water or normal saline for intravenous (IV) administration. All doses should be administered over 1 hour (54 – 75 minutes) through an IV line. See Pharmacy Manual for detailed instructions and worksheets regarding study drug preparation and administration.

Investigational product must be received at the study site by a designated person, handled and stored safely and properly, and kept in a secured location to which only the investigator and designated staff have access. Upon receipt, the investigational product should be stored according to the instructions specified on the label and in the Pharmacy Manual. Clinical supplies are to be dispensed only in accordance with the protocol. Storage conditions must be adequately monitored, and appropriate temperature logs maintained as Source data.

The investigator is responsible for the accountability of the investigational product. Records of the receipt and disposition of the investigational product must be maintained in the trial master file at the site. Records and drug supplies must be available for inspection by the study monitor.

#### **6.1.1.1 Dose Rationale**

Administration of fixed doses of MT-3724 generated early signs and symptoms of an acute innate immune response, limiting a tolerable dose to 50  $\mu\text{g}/\text{kg}/\text{dose}$  in a monotherapy setting. However, given the short  $t_{1/2}$  of MT-3724 and its mechanism of action, it is expected that the  $C_{\text{max}}$  is critical for cytotoxicity. Furthermore, rapid-onset AEs can be reduced in frequency and severity with other antibody therapies by incrementally increasing dose over time, as described below.

To mitigate safety risks, the proposed step-up dose regimen for MT-3724 will not exceed the MTD of 50  $\mu\text{g}/\text{kg}/\text{dose}$  identified in Parts 1 and 2 of the study. In addition, the maximum dose will be 1200  $\mu\text{g}$  at the 10  $\mu\text{g}/\text{kg}$  dose level, 3000  $\mu\text{g}$  at the 25  $\mu\text{g}/\text{kg}$  dose level and 6000  $\mu\text{g}$  at the 50  $\mu\text{g}/\text{kg}$  dose level.

#### **6.1.1.2 Dose Selection**

##### **Part 3:**

Two dosing cohorts are planned to complete Part 3 of the protocol to confirm the tolerable dose and schedule. A minimum of 6 subjects will be enrolled in each cohort. Following the completion of the Part 3, Part 4 of the protocol will be initiated using the regimen identified as tolerable in Part 3. Dose-limiting toxicity will be assessed during Cycle 1 of Cohorts 1 and 2. The dose and schedule are described in [Table 6-1](#).

### **Cohort 1:**

The starting MT-3724 dose for each subject will be 10 µg/kg for the first 2 doses (D1, D3) and then increased to 25 µg/kg for the remaining doses (D5, D8, D10, D12) of the first 21-day cycle and all doses of Cycle 2 (D1, D3, D5, D8, D10, D12). Dosing will then continue at 25 µg/kg weekly (D1, D8, D15), beginning with Cycle 3 ([Table 6-1](#)).

If fewer than 2/6 subjects have a DLT in Cohort 1, then the study will proceed to Cohort 2. If 2 or more subjects have a DLT in Cohort 1, the study will be stopped.

### **Cohort 2:**

The starting MT-3724 dose in each subject will be 10 µg/kg for the first 2 doses (D1, D3). The dose will then be increased to 25 µg/kg for 2 doses (D5, D8) and then the dose will be increased to 50 µg/kg for the remaining doses (D10, D12) of the first 21-day cycle and all doses of Cycle 2. Dosing will then continue at 50 µg/kg weekly (D1, D8, D15) beginning with Cycle 3 ([Table 6-1](#)).

If fewer than 2/6 subjects have a DLT in Cohort 2, then the study will continue to Part 4 using the Cohort 2 dose and schedule. If 2 / 6 subjects experience a DLT in Cohort 2, the study will continue to Part 4 using the Cohort 1 dose and schedule.

**Table 6-1. Step-up Dosing Schedule for Cohorts 1 and 2**

Day	MT-3724 Dose (µg/kg) a,b	
	Cohort 1 (n = 6)	Cohort 2 (n = 6)
Cycle 1 D1, D3	10	10
Cycle 1 D5, D8	25	25
Cycle 1 D10, D12	25	50
Cycle 2 D1, D3, D5, D8, D10, D12	25	50
Cycle 3+ D1, 8, 15 (weekly dosing)	25	50

a The total administered dose of MT-3724 must not exceed 1200 µg per infusion for the 10 µg/kg dose; 3000 µg per infusion for the 25 µg/kg dose and 6000 µg per infusion for the 50 µg/kg dose in all treatment cycles.

b Each dose of MT-3724 must be preceded by premedication administered within 60 minutes before the start of each infusion (see [Section 6.1.2](#)).

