#### **Parts 3 and 4:**

The dose of MT-3724 in all cohorts will be calculated based on the subject's baseline body weight (in kilograms [kg]). For MT-3724 dose calculation, the body weight will be measured before the first dose of MT-3724 in Cycle 1 (baseline for all subsequent assessments). If the body weight has changed by  $\geq 10\%$  from the baseline value, this will require re-calculation of MT-3724 dose or according to institutional policies should they require adjustment for any change in body weight.

**The total administered dose of MT-3724 must not exceed 1200  $\mu\text{g}$  per infusion for the 10  $\mu\text{g}/\text{kg}$  dose; 3000  $\mu\text{g}$  per infusion for the 25  $\mu\text{g}/\text{kg}$  dose and 6000  $\mu\text{g}$  per infusion for the 50  $\mu\text{g}/\text{kg}$  dose.**

The guidance for treatment modification (dose interruption / delay, dose reduction or treatment discontinuation) is presented in [Section 6.2](#).

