## 6.2 Dose Modification

The investigator may modify the MT-3724 treatment in an individual subject by:

- Dose interruption defined as changes made during the current dose (eg, temporary or permanent stop the IV infusion).
- Dose delay will be used for changes to dose schedule (eg, postpone the date of the next dose). A maximal dose delay of 14 days is allowed, a delay exceeding 14 days should be discussed with the medical monitor.
- Dose reduction (according to [Table 6-3](#))
  - Medical monitor must be notified when dose is reduced.
- Permanent discontinuation.

Refer to [Table 6-4](#) for guidance on dose modification of MT-3724 treatment (dose interruption, dose delay, dose reduction or permanent discontinuation) if deemed at least possibly related to MT-3724 by the investigator. Except where expressly prohibited (see [Section 6.1.3](#)), the use of concomitant medications is allowed at the investigator's discretion for management of toxicities.

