### 6.2.1 Dose Modification for Treatment-emergent Adverse Experiences

The following actions are recommended after any of the TEAEs listed in [Table 6-4](#) occur.

- The investigator should notify the medical monitor acting on behalf of the sponsor about the TEAE within 24 hours of the awareness.
- The investigator should monitor the subject and if necessary, perform unscheduled diagnostic procedures and therapeutic interventions, including those not specified in the study protocol.
- If a subject experienced Grade  $\geq 2$  IRR, or another Grade  $\geq 2$  hypersensitivity event, Grade  $\geq 2$  CRS or Grade  $\geq 2$  CLS, then the investigator should obtain serum samples for

cytokines, complement, and histamine as soon as possible after the TEAE onset. These samples should be marked “STAT” and shipped immediately to the central laboratory.

- MT-3724 dose may be reduced at the investigator’s discretion. See [Table 6-3](#) for recommended dose reduction steps. The number of MT-3724 dose reductions per subject is not limited, except that the reduced dose cannot be < 5 µg/kg/dose (this is the lowest dose tested in the clinic so far).
- No intra-subject escalation of MT-3724 dose is permitted after previous MT-3724 dose reduction.
- MT-3724 treatment may be **restarted** if the TEAE that previously led to treatment modification has resolved to Grade ≤1 or the subject’s baseline within the time frame deemed appropriate at the investigator’s discretion.
  - After the resolution of the TEAE, the MT-3724 dose for continued treatment may be the same or reduced, as determined according to the stopping rules (if applicable) or at the investigator’s discretion

MT-3724 treatment must be **permanently discontinued** if a TEAE that previously led to treatment modification did not resolve to Grade ≤1 or baseline within 14 days.

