**Table 6-3. Dose Reduction Steps**

Dose Reduction a	Dose µg/kg/dose		
	10	25	50
Full Dose			
First Reduction (~ 25%)	8	19	38
Second Reduction (~ 50%)	5	13	25

a Other reductions require consultation and agreement of the medical monitor.

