**Table 6-4. MT-3724 Dose Modification Guidance and Specific Management of Toxicities**

		Specific Management	MT-3724 Dose Modification a
Neutropenia or Thrombocytopenia			
ANC AND Platelet	> 500/ $\mu$ l or < 500/ $\mu$ l for < 5 days $\geq$ 25,000/ $\mu$ l		No change
ANC AND / OR Platelet	< 500/ $\mu$ l for $\geq$ 5 days, OR febrile neutropenia c $<$ 25,000 for $\geq$ 7 days with or without active bleeding, OR $<$ 50,000/ $\mu$ l for $\geq$ 7 days with clinically significant bleeding b		Decrease by 1 dose level
Infusion-related Reaction or Other Hypersensitivity Event			
IRR OR Hypersensitivity reaction	Grade $\geq$ 2	Infusion must be interrupted.	Treatment may be restarted or permanently discontinued at the investigator's discretion.  If the MT-3724 re-treatment after Grade 2 IRR is allowed, then it must occur: 
 
Only after the appropriate delay (ie, resolution of symptoms).
 
At the reduced dose and/or reduced infusion rate, where both will be chosen at the investigator's discretion.
 
After the appropriate anti-allergic prophylaxis according to the premedication guidance in this protocol (see Section 6.1.2) or the institutional guideline.
 

	Grade $\geq$ 3		MT-3724 treatment must be permanently discontinued

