**Table 6-4. MT-3724 Dose Modification Guidance and Specific Management of Toxicities**

		Specific Management	MT-3724 Dose Modification a
SCr increase $\geq$ 1.5-3.0 times above baseline or 1.5-3.0 x ULN in the absence of dehydration or bleeding			May trigger a modification of MT-3724 treatment (dose interruption, dose delay, dose reduction or permanent discontinuation) if deemed at least possibly related to MT-3724 by the investigator
Any Grade $\geq$ 3 electrolyte abnormality that does not resolve, with or without intervention, to Grade $<$ 2 within 72 hours			
Any other Grade $\geq$ 3 nonhematological toxicity excluding the following:	
 
• Nausea, vomiting, or diarrhea, if manageable with antiemetic or antidiarrheal agents within 7 days of onset
 
• Fatigue lasting <math>\leq</math> 72 hours
 
• Grade 3 laboratory abnormalities, if asymptomatic and without a clear clinical correlate
 
		
Hepatotoxicity			
AST and / or ALT OR Bilirubin	$\leq$ 5.0 x ULN (isolated) $\leq$ 1.5 x ULN (isolated)		
 
• No change in treatment
 
• Monitor subject
 

AST and / or ALT OR Bilirubin	$>$ 5 x ULN – 8.0 x ULN (for subjects enrolled with AST/ALT $<$ 3 x ULN) $>$ 1.5 x ULN – 5.0 x ULN		
 
• Temporarily or permanently (see next row) discontinue treatment
 
• Monitor subject
 
• Continue at dose reduced by 1 dose level after abnormal values resolve to Grade <math>\leq</math> 1 or baseline values
 

AST or ALT	$>$ 8.0 x ULN for any period of time (for any subject)		
 
• Permanently discontinue treatment
 

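### Infusion caps are stated only for 10, 25 and 50 µg/kg, so above 120 kg a first-step dose reduction as tabulated cuts the delivered dose by less than at or below 120 kg

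*Protocol*

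**What the plan says.** The caps appear three times in the dosing sections of the protocol, each time for the three full levels only.

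- Table 6-1, footnote a: "The total administered dose of MT-3724 must not exceed 1200" µg per infusion at 10 µg/kg, 3000 µg at 25 µg/kg and 6000 µg at 50 µg/kg.
- Section 6.1.1.1: "In addition, the maximum dose will be 1200" µg at the 10 µg/kg level, followed by the same two limits for 25 and 50 µg/kg.
- Section 6.1.1.2, Parts 3 and 4: the same three limits, after the rule that "The dose of MT-3724 in all cohorts will be calculated based on the" subject's baseline weight, with recalculation if weight changes by 10% or more.

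Sections 5.1 and 5.2 set no upper limit on body weight.

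Table 6-3 gives the reduced levels. The first step takes 10, 25 and 50 µg/kg to 8, 19 and 38; the second takes them to 5, 13 and 25. It states no cap, and Sections 6.2 and 6.2.1 and Table 6-4 add none. Section 6.2.1 does not limit the number of reductions, "except that the reduced dose cannot be" below 5 µg/kg.

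Table 6-4 sends sites to these steps in two places. For prolonged or complicated neutropenia or thrombocytopenia the action is "Decrease by 1 dose level". For intermediate liver-test elevations it is "Continue at dose reduced by 1 dose level after abnormal values resolve to Grade" 1 or baseline.

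**The concern.** A dose cap and a percentage dose reduction work together only if both use the same weight. Here the full dose stops rising at 120 kg, but nothing in the dosing sections stops the reduced dose from rising. A heavier subject who is stepped down after toxicity therefore loses a smaller share of the dose actually infused. At a high enough weight the subject loses none, or is literally prescribed more than before.

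What is at stake is the safety of individual subjects over 120 kg who need a reduction for haematological or hepatic toxicity. The response endpoint and its analysis are not involved.

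**Working it through.** **Inputs.** Full levels d = 10, 25, 50 µg/kg with caps 1200, 3000, 6000 µg (Table 6-1). First-step levels r = 8, 19, 38 µg/kg and second-step levels 5, 13, 25 µg/kg (Table 6-3). W is body weight in kg.

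**Basis of the caps.** 1200/10 = 3000/25 = 6000/50 = 120 kg. This agrees with the rationale in Section 12.1, which describes the caps as resting on a 120 kg maximum.

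**Formula.** Full dose = min(d × W, 120 × d). First-step dose = r × W, since no cap is stated for 8, 19 or 38 µg/kg. Then:

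- W ≤ 120 kg: cut = 1 − r/d, which gives 20% for 10 to 8, and 24% for 25 to 19 and 50 to 38.
- W > 120 kg: cut = 1 − (r/d)(W/120), which falls as W rises.

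| Weight (kg) | 50 to 38 (µg) | Cut, 50 to 38 and 25 to 19 | 10 to 8 (µg) | Cut, 10 to 8 |
|---|---|---|---|---|
| 120 | 6000 to 4560 | 24.0% | 1200 to 960 | 20.0% |
| 121 | 6000 to 4598 | 23.4% | 1200 to 968 | 19.3% |
| 130 | 6000 to 4940 | 17.7% | 1200 to 1040 | 13.3% |
| 140 | 6000 to 5320 | 11.3% | 1200 to 1120 | 6.7% |
| 150 | 6000 to 5700 | 5.0% | 1200 to 1200 | 0% |
| 160 | 6000 to 6080 | −1.3% | 1200 to 1280 | −6.7% |

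The cut reaches zero at 6000/38 = 3000/19 = 157.9 kg, and at 1200/8 = 150 kg.

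**Delivered µg/kg.** Expressing the dose per kg of actual weight does not change the result. At 130 kg the capped full dose is 6000/130 = 46.2 µg/kg, so the step is 46.2 to 38, again 17.7%. The Table 6-3 percentages describe nominal levels only.

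**When 10 to 8 can apply.** The 10 µg/kg level is used only on Cycle 1 Days 1 and 3. A reduction follows toxicity, so 8 µg/kg can first apply on Day 3. The neutrophil and platelet duration triggers in Table 6-4 (at least 5 and 7 days) could not normally be met by then; febrile neutropenia or a hepatic event could.

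**Second steps.** 50 to 25 is 50% at every weight, because 25 µg/kg has its own cap. 25 to 13 falls from 48% to 43.7% at 130 kg (1 − 1690/3000) and 35% at 150 kg (1 − 1950/3000). 10 to 5 falls from 50% to 45.8% (1 − 650/1200) and 37.5% (1 − 750/1200).

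**Other readings.** If the parent level's cap also limits the reduced dose, nothing changes below 157.9 kg (150 kg for 8 µg/kg), and the cut is 0% above. If weight is capped at 120 kg at every level, the cut stays at 20%, 24% and 24%. Only this last reading removes the problem. Against it, the tabulated 38 µg/kg dose is too high by 4940 − 4560 = 380 µg (8.3%) at 130 kg and 5700 − 4560 = 1140 µg (25%) at 150 kg.

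**Reach.** The documents give no weight distribution. If 0% to 5% of about 113 subjects exceed 120 kg (an assumption), that is 0 to 113 × 0.05 = 5.65, or about 6. Only those who also need such a reduction would be affected.

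**The case against.** The strongest reply is that a site is not left alone with Table 6-3. Section 6.2.1 calls the steps recommended, and the note to Table 6-4 calls its contents recommendations. Footnote a to Table 6-4 describes one level as roughly 25% to 33%, with actual amounts set after consultation with the sponsor and medical monitor. Section 6.2 adds "Medical monitor must be notified when dose is reduced". A 5% cut at 150 kg would visibly conflict with footnote a. Section 6.1.1 also refers to preparation worksheets in the Pharmacy Manual, which is not among the documents and may hold a 120 kg rule. All of this stands. A reader might infer that sites would under-reduce; the text supports only that they could. None of these controls states a cap, however, and the table is the only place with exact reduced levels.

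A second reply is that the only stated link between total dose and harm concerns capillary leak syndrome (Section 12.1). No passage says that total µg drives haematological or hepatic risk, and at 130 kg a reduced subject still receives 38 µg/kg. This is fair as to proven harm. It does not explain why the same one-level instruction should remove 24% at 120 kg and 5% at 150 kg.

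Three stronger readings are tempting and should be set aside:

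- **Grade 2 capillary leak syndrome.** Table 6-4 gives it a separate minimum cut of 25%, so it is not part of this point.
- **The 20% and 24% at or below 120 kg.** These fall short of footnote a's range because of rounding. The missing cap does not cause that and the fix does not cure it.
- **The change log.** That 120 kg is named there and not in Section 6 is not an error in itself. It is useful as evidence of what the sponsor intended.

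**Conclusion.** The point holds as a minor safety clarification. No cap is stated for 8, 19, 38, 13 or 5 µg/kg. Followed literally, the first-step cut shrinks at every weight above 120 kg, reaches zero at 157.9 kg (150 kg for 10 to 8) and then reverses. The arithmetic rests only on the printed caps, the printed levels and weight-based dosing, so it is firm.

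The practical effect is uncertain. It depends on whether any subject over 120 kg needs a reduction, on what the Pharmacy Manual says, and on how the consultation is used. Possibly nobody would be affected. A reader might also infer that the trial's conclusions are at risk. They are not: the response endpoint, its decision rule and the analysis sets are untouched.

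**What to change.** State in Section 6.1.1.2, and in a footnote to Table 6-3, that a dosing weight of at most 120 kg is used at every dose level, including reduced levels. The caps (level × 120) are then:

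- 8 µg/kg: 960 µg
- 19 µg/kg: 2280 µg
- 38 µg/kg: 4560 µg
- 13 µg/kg: 1560 µg
- 5 µg/kg: 600 µg

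The 3000 µg cap at 25 µg/kg is unchanged. The first step becomes 20%, 24% and 24% at every weight.

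Add to Section 6.2.1 that the 5 µg/kg floor uses the same capped weight. Otherwise the 600 µg cap would breach the floor above 120 kg: 600/130 = 4.6 µg/kg and 600/150 = 4.0 µg/kg of actual weight. Receiving less than 5 µg/kg of actual weight at the floor is the one small downside for these subjects.

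The cost is one sentence, one footnote and one phrase, plus a check that the Pharmacy Manual agrees.
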